3.3 Research questions

What is the proportion of participants who progressed as planned or successfully complete the program at 3, 6, and 10 years after start of the programme? What is the societal business case of the programme and what opportunities for improvement can be identified to optimize its sustainability through a qualitative analysis of the impact on both participants and hospital departments? To what extent do competencies across different domains provide insight into when a participant may require additional support? To what extent do conscious or unconscious racial microaggressions occur in the workplace and what opportunities exist to address and mitigate the unconscious form?

4. Study design

4.1 Mono- or multicenter study.	Monocenter study 	Multicenter study 
--	--	--

4.2 Retrospective study or prospective study		Retrospective study 	Prospective study 
4.3 Cross-sectional or follow-up study		Cross-sectional study 	Follow-up study 
4.4 Quantitative or qualitative study		Quantitative study 	Qualitative study 
4.5 Pilot or explorative study?	Not applicable 	Pilot study 	Explorative study 

Explain why it is a pilot or explorative study.

This study can be considered both a pilot and an exploratory study for several reasons. First, the program under investigation was not originally conceived as a research project but as an improvement initiative, meaning that the data were collected prospectively in a real-world setting without predefined hypotheses. Second, the number of participants is still limited, and the program is in an early stage of implementation across centers, which makes the findings preliminary by nature. Third, the primary aim is descriptive, examining proportions of participants who progress through or complete different phases of the program, rather than testing causal relationships. In addition, secondary analyses, such as the societal business case and the qualitative assessment of program impact, are exploratory in character, intended to generate insights and hypotheses for future, more definitive evaluations. Taken together, these features justify the classification of the study as a pilot and exploratory investigation, providing essential groundwork for larger-scale, hypothesis-driven research.

In case of a pilot study, what are the concrete follow-up plans.

The concrete follow-up plan is to expand the program to hospitals at the national level and to integrate data from these additional sites into the analysis. This will allow for larger-scale evaluation, validation of findings across different contexts, and the development of more robust evidence on program effectiveness. Ultimately, the pilot provides the foundation for a nationwide multicenter study aimed at informing sustainable policy and implementation.

5. Population

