The primary outcome: the proportion of participants who either progressed as planned, successfully completed the program by obtaining a (conditional) certificate of professional competence, or transitioned to employment as care assistants.

Secondary outcomes include:

- a societal business case and a qualitative analysis to assess the impact of the program on participants and departments
- the influence of competencies on the need for additional guidance
- potential unconscious and conscious racial microaggression in the workplace

Factors considered as potential confounders are:

- sociodemographic characteristics: age, gender, time since arrival in the Netherlands, and family situation
- educational and professional background: level and type of nursing qualification, years of work experience, and previous additional training
- language and cognitive capacity: baseline Dutch and English proficiency, learning capacity as assessed by the study skills test, and motivation and initiative
- programme-related/contextual factors: hospital/department, differences in mentorship/guidance during integration, regional labor market demand, adaptations or optimizations implemented within the program over time

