- Exit position: premature exit, exit as healthcare assistant, exit as BIG-registered nurse (or achievement of a comparable qualification at the paramedical level with a similar background)
- At exit: healthcare assistant or nurse – type of contract and number of hours: 1 Temporary (eg 1 year); 2 Permanent
- Start date as fully qualified nurse (possibly including onboarding period)
- Program underway and on track? program successfully completed; program still in progress and proceeding as planned; dropped out during the medical language program phase; dropped out during the assistant nurse phase due to insufficient background to continue; decided to stop BIG trajectory during assistant nurse phase and continue/start working as a care assistant; Other

For secondary outcomes and other outcomes:

Data to be completed by newcomer

- Years of education completed
- Country of training
- Attempts to have diploma recognized in the Netherlands
- Level achieved according to the diploma evaluation: A level that corresponds in Dutch terms to: diploma from senior secondary vocational education (MBO), qualification level 4, in nursing and care; 2 years of a nominal 4-year bachelor's program in higher professional education (HBO) in nursing; degree of bachelor in higher professional education (HBO) in nursing; degree of master in higher professional education (HBO) in nursing; other level
- Place of work experience: hospital, nursing home or care home, home care, other
- Years of work experience
- Last country you worked in before arriving in the Netherlands?
- Experience in the following types of hospital departments (multiple answers possible)
- Nursing tasks for which you are qualified: measuring blood pressure, wound care, removing stitches/sutures, preparing medication, venous puncture, inserting IV (intravenous) line, inserting urinary catheter, inserting nasogastric tube, resuscitation / CPR (cardiopulmonary resuscitation)
- As a nurse in the hospital, you have day, evening, and night shifts. Each shift lasts 8 hours. What is your attitude towards evening and night shifts? No problem, I am used to working these shifts; It will take some getting used to, but I think I can manage this with my private life; It is difficult to reconcile with my private life
- Years living in the Netherlands at time of entry
- Socioeconomic status at the time of entry

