- Income level (if employed): 1 Less than or equal to minimum wage; 2 Comparable to a healthcare assistant's income; 3 Higher than a healthcare assistant's income
- Receiving healthcare allowance: 1 Yes; 2 No
- At entry EuroQol EQ-5D-5L questionnaire
- At exit EuroQol EQ-5D-5L questionnaire
- Residence and work permit for the Netherlands
- Basis for a residence permit? asylum; residence with partner; study (temporary residence permit); other

- Have you already had a 'Further Hearing' with the IND?
- Completed language/integration course?
- English/ Dutch language proficiency level: 1 A2 to B1; 2 B1 to B2; 3 B2
- Initials, surname, age, email address, phonenumber, current address or name of the shelter
- Domains: self-efficacy (resilience, flexibility, and adaptability; motivation and self-awareness; curiosity and lifelong learning; reliability and attention to detail); working with others (empathy and active listening; leadership and social influence); Ethics (cultural competence); physical skills (manual dexterity, endurance, and precision in the professional field); management skills (quality control); technological literacy (Appendix 4)
- Modified Racial Microaggressions Scale (RMAS) including 6 subscales: invisibility, criminality, dysfunctional culture, sexualization, foreigner/not belonging and environmental microaggressions. This questionnaire was developed by Torres-Harding et al⁸ and modified by King et al⁹ and appears to be an appropriate tool to assess this on the workplace¹⁰ (appendix 6).

Data to be completed by language center:

- Suitable candidate for 'Newcomers in Their Strength 2.0' program (based on intake)? No, the candidate is definitely unsuitable; yes, this is a suitable candidate; there is doubt about the candidate's suitability
- Score Study Skills Test
- Optional 2nd Score Study Skills Test
- Reason for taking 2nd Study Skills Test?

Data to be completed by study coordinator:

- Is the candidate a refugee or asylum seeker?
- Date of introductory meeting
- Candidate enrolled in newcomers program? no; yes; no, but may be considered in the future if the candidate develops appropriately

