
9.3.2 If applicable: not all items in the above list of pseudonymization requirements apply to my study. Please elaborate on the reason for this and the alternative solutions.
 
All pseudonymization requirements apply to this study. The only clarification is that during the data collection phase direct identifiers and research data are temporarily handled together by the study coordinator to complete essential outcome information. Once these data are recorded direct identifiers are removed and replaced by a study code with the code list stored separately and securely. From that point onward, all requirements are fully met: direct identifiers are stored separately, pseudonymized data are used for analysis only and access is restricted to the Principal Investigator and authorized study delegates. Data roles and responsibilities are documented in the delegation log
	

10. FAIR Data and Data Sharing

10.1 FAIR data The following statements concern FAIR data, which is the UMCG policy. Please note that FAIR is not the same as Open Access.			
Data will be made findable by including the description of the study (and type of data (i.e. metadata) in the UMCG FAIR data catalogue and other discipline specific catalogue(s).	Yes 	No 	
If 'no' is answered on the above question , please elaborate on the reason for this. NA			

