11.7 Biomaterials check-list	
11.7.1 The following are requirements for the use of biomaterials, please mark all that apply:	
• Only biomaterials required to answer the research question(s) will be collected (dataminimalisation)	
• The biomaterials will be anonymized or pseudonymized according to laws, guidelines and (if applicable) SOPs	
• Biomaterials can only be accessed by the Principal Investigator and study delegates, after authorization by the Principal Investigator	
• Biomaterials will be stored 15 years after the study is completed	
11.7.2 Not all items in the above section apply to my study. Please elaborate on the reason for this and the alternative solutions. NA	

12. Burden, Risks & Benefits

12.1 Burden Is there a (potential) burden for the participant as a result of participating in this study? For example: feeling tired after performing tests, reliving bad memories.	Yes, minimal burden 	Yes, more than minimal burden 	No 

If yes, please explain what the burden is/might be
 
The potential burden for participants is minimal. Participation involves completing a short questionnaire of approximately 10 minutes aimed at assessing professional competencies. All other required information overlaps with data that participants are already asked to provide as part of the regular eligibility assessment for the program.
 
Clarify what is done to alleviate the burden
 
To alleviate the burden, data provided by participants for the regular program eligibility assessment (e.g. background information) are directly and secondarily used for research purposes as well. In this way, no duplicate data collection is required, and participation in the study does not add substantially to the effort already needed for program entry
			
12.2 Risk Does the participant run a risk of injuries and/or other discomfort as a result of participating in this study? For example: risk of falling while doing exercises	Yes, minimal risk 	Yes, more than minimal risk 	No 

If yes, please explain what the risk entails. NA Clarify what is done to alleviate the risk. NA		

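### The microaggression question separates conscious from unconscious forms, but the only planned measure does not record the actor's awareness and has no stated time point

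*Protocol*

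**What the plan says.** Protocol 3.3 asks: "To what extent do conscious or unconscious racial microaggressions occur in the workplace", and goes on to ask how the unconscious form could be addressed and mitigated. Section 3.2 lists the matching secondary outcome as "potential unconscious and conscious racial microaggression in the workplace".

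Section 6.1 names one instrument for this, in the block headed "Data to be completed by newcomer": the "Modified Racial Microaggressions Scale (RMAS) including 6 subscales: invisibility, criminality, dysfunctional culture, sexualization, foreigner/not belonging and environmental microaggressions". It adds that the modified scale seems suitable for workplace use. Appendix 6 prints the original questions and states that the modified version will be the one used. It does not print the modified wording or a recall period. In the same block of 6.1 the EQ-5D-5L is listed once at entry and once at exit. No time is given for the RMAS.

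On burden, 12.1 says: "Participation involves completing a short questionnaire of approximately 10 minutes aimed at assessing professional competencies". It then states that everything else required is already covered by the eligibility assessment.

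On data handling, 9.3.2 says that during collection "direct identifiers and research data are temporarily handled together by the study coordinator".

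**The concern.** A research question that names two forms of behaviour and asks how to reduce one of them needs data that tell the two apart. A scale filled in by the recipient reports what was experienced. It does not observe what the other person knew or intended. If nothing else is collected, the report can describe how often microaggressions were perceived, but it has no basis for statements about the unconscious form in particular.

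The timing gap is a separate matter. Workplace experience can be reported only after work has begun. If the RMAS were sent out with the registration material, as 12.1 can be read, its answers would concern life before the programme's hospitals. Results labelled as workplace findings would then describe another setting and period.

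A smaller issue is disclosure. Answers about colleagues' behaviour are sensitive, and the protocol makes no exception for them in the period when names and data are held together.

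**Working it through.** No sample size, power or error rate enters this point, so the check sets the question beside the instrument, its timing and its handling.

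**1. Can the instrument separate the two forms?**
- Required (3.2, 3.3): conscious and unconscious microaggressions, with mitigation of the unconscious form.
- Available (6.1): 6 subscales, each defined by the content of the experience, such as being overlooked, being treated as a criminal or being seen as a foreigner. Subscales that record the actor's awareness: 0 of 6.
- Original items (Appendix 6): they describe what others assume, suggest or do as the respondent perceives it, or how few people of the respondent's background are present. None asks whether the other person was aware of it.
- Other sources (Appendix 7): the printed participant questions concern satisfaction with the programme and contain none on microaggressions. The buddy questions ask for general ratings of interaction, support and patients' attitude. None concerns awareness.

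No planned source contains the distinguishing variable.

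**2. Is the measurement placed during work?**
- Stated administration times in 6.1: EQ-5D-5L 2, RMAS 0.
- Section 12.1 allows for one competency questionnaire of about 10 minutes, and assigns everything else to eligibility. The competency questions printed in Appendix 4 contain no RMAS items. On 12.1's wording the RMAS is therefore either completed at eligibility or left out of the account.
- Eligibility comes before ward work. In Appendix 2, participants start as assistant nurses only after a vocational language course of about 3 to 3.5 months.
- Section 12.1 cannot be literally complete, because an EQ-5D-5L at exit cannot be part of an entry assessment. Sections 6.1 and 12.1 contradict each other and must be reconciled.

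**3. Who sees the answers?**
- Section 9.2 ticks pseudonymisation during collection. Its explanation, and 9.3.2, say that codes replace identifiers only once the required data are complete. BIG registration is given as an example of those data, so the period can be long.
- In 6.1 the study coordinator also records enrolment, reason for rejection, extra guidance and cause of dropout. No separate route is described for the RMAS. The Regioplan survey in Appendix 7, by contrast, was promised anonymous storage.

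**4. How much can still be collected properly?**
- Section 6.3 projects 98 + 80 = 178 further participants; with the 49 already enrolled (7.2.2.2) that makes 178 + 49 = 227.
- Share still to come at the upper projection: 178 / 227 = 78%.
- Share still to come at the lower projection of 159: (159 − 49) / 159 = 110 / 159 = 69%.

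**The case against.** Several points on the other side have weight.

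- *The question may mean both forms taken together.* Section 3.1 states the aim without any split, and no section plans to estimate a ratio. This stands in part: an overall frequency needs no distinction. The clause on mitigating the unconscious form does need it, and 3.2 names both forms as an outcome.
- *The qualitative part could supply it.* It could, but none of the printed questions asks about it.
- *The modified scale may be framed for the workplace.* That is possible. Its wording is not printed, and 6.1 describes it as suitable. A well-timed modified RMAS could describe perceived frequency at work, so a reader who infers that the whole question is unanswerable goes too far.
- *Section 12.1 is weak evidence on timing.* This is correct. It is contradicted by the exit EQ-5D-5L, and 3.2 and 3.3 both place the construct at work. The documents do not show that the RMAS will be given before ward work, only that no time is stated and that the one section bearing on it points the wrong way.
- *The coordinator.* A reader might infer that answers go to someone whose programme decides the participant's progress. The text does not say so: the coordinator's items are records, and professional competence is decided by an external body (6.1). Identified handling is a possible source of under-reporting, of unknown size, and does not by itself defeat the question.
- *Burden.* A reader might take the 34 original items printed in Appendix 6 as the load on participants. The length of the modified scale is not given, so that count does not establish it.
- *The study is a pilot and exploratory.* This lowers the stakes, but a descriptive aim still needs a measure of what it describes.

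**Conclusion.** The point holds in two parts. First, the conscious/unconscious distinction cannot be drawn from the planned data: 0 of 6 subscales and no printed survey question record the actor's awareness. This rests on the modified RMAS having the 6 subscales named in 6.1 and on the printed surveys being the ones used. Second, the RMAS has no stated time point, and 12.1 read literally would place it before any work in the programme's hospitals while contradicting 6.1 on the exit EQ-5D-5L. Timing and burden are for the protocol to settle and would not normally be left to an analysis plan.

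The reach is one secondary research question out of four; the primary outcome is untouched. The disclosure risk is plausible, but nothing in the documents allows it to be quantified. The changes should be made before RMAS collection goes further, because on the protocol's own projections 69% to 78% of participants are still to enrol.

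**What to change.** - **Question and outcome (3.2, 3.3).** Restate both as the frequency of perceived racial microaggressions at work, by RMAS subscale. Either drop the conscious/unconscious distinction, including the clause on mitigating the unconscious form, or keep it for the qualitative part and add questions that address it.
- **Timing and setting (6.1, Appendix 6).** Give the modified RMAS at fixed times after ward start, for example 6 months and exit, with the participating hospital as the reference setting. Print the modified wording and the recall period.
- **Burden (12.1).** Include the RMAS and the exit EQ-5D-5L, so that 12.1 agrees with 6.1.
- **Handling (9.2, 9.3.2).** Collect RMAS answers through a separate link under a study code that neither the coordinator nor the hospital can see. A code is preferable to full anonymity because it keeps a participant's repeated answers linkable.

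The cost is protocol wording, one separate coded survey link, someone outside the coordinator's role to hold its key, and slightly more questionnaire time for participants.

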5.1 Research participants		
Healthy volunteers		
Patients		
5.2 Participant classification		
Participants ≥ 16 years		
Children between 12 and 16 years		
Children < 12 years		
Explain purpose limitation ('doelbinding' in Dutch) if you plan to include minors below 16 of age. This means that this data may only be gathered if participation of that age group is utterly essential (Dutch: persoonsgegevens alleen verzamelen met een gerechtvaardigd doel waarvoor die leeftijdsgroep noodzakelijk is). NA		
5.3 Incapacitated adults		
Participants can be incapacitated/decisionally impaired adults	Yes 	No 

If yes, explain purpose limitation ('doelbinding' in Dutch). This means that this data may only be gathered if participation of this group is utterly essential (persoonsgegevens alleen verzamelen met een gerechtvaardigd doel waarvoor deze groep noodzakelijk is).

NA

5.4 Inclusion and exclusion criteria

- Inclusion criteria:

- refugee or migrant with a nursing background or other paramedical background and sufficient indications that the relevant hospital department is prepared to cooperate in a fast-track integration trajectory
- holding at least a diploma equivalent to the Dutch MBO-4 level
- having practical experience, preferably in a hospital setting
- residence in one of the three northern provinces
- sufficient learning capacity to participate in a language course at the University of Groningen's Language Centre (LC) based on the intake and, if available, a study skills test
- a successful application interview

- Exclusion criteria:

- diploma lower than Dutch MBO-4 level
- refugee or migrant with a background as medical doctor

6. Study data, and analysis

